#### 7.1.6.2. Summary of Deaths

A summary (number and percentage of subjects) of deaths will be provided by presenting the following categories:

- All deaths
- Deaths within 30 days of the last dosing of study drug
- Deaths beyond 30 days of the last dosing of study drug

## 7.2. Laboratory Evaluations

Laboratory data collected during the study will be analyzed and summarized using both quantitative and qualitative methods. Summaries of laboratory data will be provided for the Safety Analysis Set and will include data collected up to the last dose of study drug plus 30 days for subjects who have permanently discontinued study drug, or all available data at the time of the database snapshot for subjects who were ongoing at the time of an interim analysis. The analysis will be based on values reported in conventional units. When values are below the LOQ, they will be listed as such, and the closest imputed value will be used for the purpose of calculating summary statistics as specified in Section 3.7. Hemolyzed test results will not be included in the analysis, but they will be listed in by-subject laboratory listings.

A by-subject listing for laboratory test results will be provided by subject ID number and visit in chronological order for hematology and serum chemistry separately. Values falling outside of the relevant reference range and/or having a severity grade of 1 or higher on CTCAE severity grade will be flagged in the data listings, as appropriate.

### 7.2.1. Graded Laboratory Values

CTCAE Version 4.03 will be used to assign toxicity grades (0 to 4) to laboratory results for analysis. Grade 0 includes all values that do not meet the criteria for an abnormality of at least Grade 1. For laboratory tests with criteria for both increased and decreased levels, analyses for each direction (ie, increased, decreased) will be presented separately. Local labs will be graded based on the central lab normal ranges with in-house macro. For the event that both central and local lab results are collected in the clinical database, the worst toxicity grade will be used for the summary of lab toxicities. All central and local laboratory values will be listed.

#### 7.2.1.1. Treatment-Emergent Laboratory Abnormalities

Treatment-emergent laboratory abnormalities are defined as values that increase at least 1 toxicity grade from baseline at any postbaseline time point, up to and including the date of last dose of study drug plus 30 days for subjects who permanently discontinued study drug, or the last available date in the database snapshot for subjects who were still on treatment at the time of an interim analysis. If the relevant baseline laboratory value is missing, any abnormality of at least Grade 1 observed within the time frame specified above will be considered treatment emergent.

#### 7.2.1.2. Summaries of Laboratory Abnormalities

The following summaries (number and percentage of subjects) for laboratory abnormalities will be provided by lab test:

- Baseline grade (Grade 0 to 4 separately, Grade 3 or 4, Grade 1 to 4, and Missing)
- Worst treatment-emergent laboratory abnormalities postbaseline grade (Grade 1 to 4 separately, Grade 3 or 4, and Grade 1 to 4)

The summary of the baseline abnormalities will use the number of subjects in the Safety Analysis Set as the denominator. The summary of the worst treatment-emergent laboratory abnormalities postbaseline is the number of subjects with nonmissing postbaseline values up to 30 days after the last dosing date of the study drug.

A by-subject listing of treatment-emergent Grade 3 or 4 laboratory abnormalities will be provided by subject ID number and visit in chronological order. This listing will include all test results that were collected throughout the study for the lab test of interest, with all applicable severity grades displayed.

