- c) The previously BCR treated patients will be limited to subjects with CLL (other BCR targeted therapies may be accepted after approval of the medical monitor) only in the context of this cohort are Richter's transformation eligible.
 - i) CLL subjects whom have had more than 1 BCR targeted therapy will be enrolled into the cohort of the most recent treatment ibrutinib or idelalisib received prior to progression.

- 5) Presence of radiographically measurable progressive disease as defined using Cheson criteria for NHL, and iNHL and by IWCLL criteria for CLL; lymphadenopathy or extranodal lymphoid malignancy (defined as the presence of ≥ 1 lesion that measures ≥ 2.0 cm in the longest diameter [LD] and ≥ 1.0 cm in the longest perpendicular diameter [LPD] as assessed by CT or MRI);
 - a) Subjects with LPL/WM who do not have radiographically measurable progressive disease must have a monoclonal serum IgM $\geq 2x$ ULN as verified by serum protein electrophoresis (SPEP) and with lymphoplasmacytic marrow involvement are eligible. LPL/WM enrollment is limited to those sites which have cryoglobulin analysis capabilities
- 6) All acute toxic effects of any prior antitumor therapy resolved to Grade ≤ 1 before the start of study drug (with the exception of alopecia [Grade 1 or 2 permitted], neurotoxicity [Grade 1 or 2 permitted], or bone marrow parameters [Grade 1, 2, or 3 permitted])
- 7) Karnofsky performance status of ≥ 60
- 8) Life expectancy of at least 3 months
- 9) Required screening laboratory data (within 5 weeks prior to administration of study drug) as shown in **Table 4-1**. *Note: Confirmation should be considered for out-of-range values to determine if the abnormality is real or artifactual. Values used for screening must be obtained within the screening period and should be the most recent measurement obtained. Subjects with any degree of neutropenia, thrombocytopenia, or anemia with documentation that it is due to malignancy may enroll.*

Table 4-1. Required Screening Laboratory Values

Organ System	Parameter	Required Value
Hematopoietic	ANC	$\geq 0.5 \times 10^9/L$
	Platelets	$\geq 50 \times 10^9/L$
	Hemoglobin	$\geq 80 \text{ g/L (8.0 g/dL)}$
Hepatic	Serum total bilirubin	$\leq 1.5 \times \text{ULN}$ (unless elevated due to Gilbert's syndrome or hemolysis)
	Serum ALT	$\leq 2.5 \times \text{ULN}$
	Serum AST	

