8.5.3.4. Laboratory Evaluations

All laboratory data will be listed. Summaries of laboratory data will be based on observed data and will be reported using conventional units. The focus of laboratory data summarization will be on treatment-emergent laboratory abnormalities. A treatment-emergent laboratory abnormality is defined as an abnormality that, compared to baseline, worsens by ≥ 1 grade in the period from the first dose of study treatment to 30 days after the last dose of study treatment. If baseline data are missing, then any graded abnormality (ie, an abnormality that is Grade ≥ 1 in severity) will

be considered treatment emergent. Laboratory abnormalities that occur before the first dose of study treatment or > 30 days after the subject is discontinued from study treatment will be included in data listings.

Hematological, serum biochemistry, and coagulation data will be programmatically graded according to a Gilead modified CTCAE severity grade, when applicable. For parameters for which a CTCAE scale does not exist, reference ranges from the central laboratory will be used to determine programmatically if a laboratory parameter is below, within, or above the normal range for the subject's age, sex, etc.

Hematological, serum biochemistry, and coagulation results and their changes from baseline will be summarized. Summary tables will be presented for each relevant assay to show the number of subjects by CTCAE severity grade with corresponding percentages. For parameters for which a CTCAE scale does not exist, the frequency of subjects with values below, within, and above the normal ranges will be summarized. Subjects will be characterized only once for a given assay, based on their worst severity grade observed during a period of interest (eg, during the study or from baseline to a particular visit).

Shift tables for hematology, serum biochemistry, and coagulation will also be presented by showing change in CTCAE severity grade from baseline to each visit. For parameters for which a CTCAE scale does not exist, shift tables will be presented showing change in results from baseline (normal, low and high [or abnormal]) to each visit (normal, low and high [or abnormal]). Tables will be prepared to show frequencies adjusted for baseline values; for this frequency, subjects with the same or worse toxicity grade at baseline are not considered.

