#### **7.7. Changes from Protocol-Specified Safety Analyses**

There are no deviations from the protocol-specified safety analyses.

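### The SAP leaves out the protocol's baseline-adjusted laboratory frequencies without declaring it, so its only treatment-emergent percentages mix subjects at risk with subjects already at that grade

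*SAP*

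**What the plan says.** **Protocol 8.5.3.4** does two things. It defines the event: "A treatment-emergent laboratory abnormality is defined as an abnormality that, compared to baseline, worsens by" at least one grade, within 30 days of the last dose. In its paragraph on shift tables it also commits to tables of frequencies adjusted for baseline values, and specifies that "for this frequency, subjects with the same or worse toxicity grade at baseline are not considered".

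**SAP 7.2.1.1** keeps the same event definition: "values that increase at least 1 toxicity grade from baseline at any postbaseline time point". If baseline is missing, any abnormality of Grade 1 or more counts.

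**SAP 7.2.1.2** lists two summaries for each test: baseline grade, and "Worst treatment-emergent laboratory abnormalities postbaseline grade (Grade 1 to 4 separately, Grade 3 or 4, and Grade 1 to 4". On the denominator of the second it says: "The summary of the worst treatment-emergent laboratory abnormalities postbaseline is the number of subjects with nonmissing postbaseline values", up to 30 days after the last dose. The word "denominator" is absent from that sentence and has to be carried over from the one before it. Nothing excludes subjects by baseline grade.

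**SAP 7.2.2** adds a shift table from baseline grade to worst post-baseline grade. No baseline-adjusted frequency appears anywhere in SAP 7.2.

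**SAP 7.7** states: "There are no deviations from the protocol-specified safety analyses".

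**The concern.** The population makes the omitted adjustment relevant. Under Protocol 4.2.1, criterion 6 admits marrow parameters at Grades 1 to 3, and the note to criterion 9 says: "Subjects with any degree of neutropenia, thrombocytopenia, or anemia with documentation that it is due to malignancy may enroll". Protocol 5.3.6 makes provision for subjects who enter with Grade 3 or 4 abnormalities caused by their malignancy. Some subjects will therefore start at grades from which they cannot contribute an event to certain rows.

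SAP 3.2 sets cohorts and dose levels side by side, and the dose levels hold about 20 subjects each. Two columns with the same risk among subjects who could still have the event will show different percentages if their baseline cytopenia differs. The protocol's adjusted frequency is the table that would separate the two explanations. Laboratory abnormalities are part of the secondary safety endpoint, and a reader who relies on SAP 7.7 would not know that the table had been dropped.

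**Working it through.** The documents give no laboratory abnormality rate and no distribution of baseline grades, so there is no planned figure to reproduce. All rates and shares below are assumptions; only the group size of 20 (CLL dose levels, Protocol 8.7) and the cohort size of 40 come from the plan.

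**1. Is the table really missing?** Protocol 8.5.3.4 lists worst-grade summaries, shift tables by visit, and baseline-adjusted frequencies. SAP 7.2 lists baseline grade, worst treatment-emergent grade, and a shift to worst grade only. The adjusted frequencies have no counterpart, and the by-visit shift has been reduced as well. Where the SAP drops other analyses because the report will be synoptic, it says so (SAP 6.3 for efficacy sensitivity analyses, SAP 9 for pharmacodynamics). SAP 7.7 makes no such statement.

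**2. Single-grade row g.** Let N be subjects with a post-baseline value, b the share with baseline grade g or worse, and r the proportion of the others whose worst grade is g.
- Events = r x N(1-b), because subjects at g or worse cannot rise to g.
- SAP percentage = r(1-b).
- At-risk rate / SAP percentage = 1/(1-b).

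| Assumed b | SAP percentage if r = 30% | Ratio |
|---|---|---|
| 0% | 30% | 1.00 |
| 10% | 27% | 1.11 |
| 20% | 24% | 1.25 |
| 30% | 21% | 1.43 |
| 40% | 18% | 1.67 |
| 50% | 15% | 2.00 |

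In dose arms of 20 with 2 versus 8 such subjects, the same r gives 18 x 0.30/20 = 27% and 12 x 0.30/20 = 18%.

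**3. Pooled Grade 3 or 4 row.** A baseline Grade 3 subject who reaches Grade 4 has risen one grade and counts. Only baseline Grade 4 subjects cannot. Take N = 40, with 10 at baseline Grade 3 and 30 below it, and a 20% chance that a subject below Grade 3 reaches Grade 3 or 4. The adjusted rate, leaving out baseline Grade 3 or worse, is 20%. The SAP percentage is (30 x 0.20 + 10 x p)/40, where p is the chance of going from Grade 3 to 4.

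| p | SAP percentage | Adjusted rate |
|---|---|---|
| 0% | 6/40 = 15.0% | 20% |
| 10% | 7/40 = 17.5% | 20% |
| 20% | 8/40 = 20.0% | 20% |
| 30% | 9/40 = 22.5% | 20% |
| 40% | 10/40 = 25.0% | 20% |

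The direction depends on whether p is below or above the risk in subjects starting under Grade 3.

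**4. Can the adjusted rates be rebuilt?** An invented shift table for 40 subjects has 33 with baseline below Grade 3, 6 at Grade 3 and 1 at Grade 4. Three subjects reach Grade 3 and two reach Grade 4 from below Grade 3; two more go from Grade 3 to 4.
- Grade 3 row: SAP 3/40 = 7.5%; at risk 3/33 = 9.1%.
- Grade 4 row: SAP (2+2)/40 = 10.0%; at risk 4/39 = 10.3%.
- Pooled row: SAP (3+2+2)/40 = 17.5%; adjusted (3+2)/33 = 15.2%.

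The at-risk figures come straight from the shift table. In this example the pooled SAP figure is the higher one.

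**The case against.** The strongest defence is that events over all subjects tested is a correct proportion of those tested and a common convention. The protocol names no denominator for its treatment-emergent summary, so the SAP's percentage is not an error. That stands, and it is why the current column should stay.

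A second defence is that the protocol does not say that the subjects left out leave the denominator. If they are merely not counted as events, the treatment-emergent rule already achieves most of that. The wording does allow this reading, but the same section has already defined treatment-emergent as a worsening of at least one grade, so it would make the sentence nearly redundant. The sentence also removes subjects, not events. Exclusion from the frequency altogether is the more natural reading; if the sponsor means the other, the SAP should say so.

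Third, the information is mostly there: baseline grade is tabulated, the shift table is kept, and SAP 7.2 probably supplies its analysis set and 30-day window, although SAP 7.2.2 repeats neither. The analyses are descriptive, and the futility rule uses progression-free survival only. This limits the consequence, but leaves a promised table to be rebuilt by hand for each test and cohort.

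A reader might go further and infer that the Grade 3 or 4 percentages are biased downward throughout. The documents do not support that: under SAP 7.2.1.1, Grade 3-to-4 worsening counts in the pooled row, and step 3 shows that the figure can move either way. Applying the 27% versus 18% contrast to the pooled row would require 10% to 40% of a group to enter at Grade 4, for which the documents give no basis.

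**Conclusion.** The omission holds on the text: the protocol's baseline-adjusted laboratory table is not in the SAP, and SAP 7.7 is wrong to declare no deviation. This rests on the more natural reading of the protocol sentence.

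The numerical consequence is limited and conditional. In single-grade rows the SAP percentage falls short of the at-risk rate by the factor (1-b): no effect if nobody starts at or above that grade, half if 50% do. The actual b is unknown. In the pooled row the problem is one of interpretation rather than a bias of known sign, since new severe abnormalities and worsening of existing ones are added together. It would be too strong to say that the adjusted rates are lost, or that the existing denominator is invalid. The point is worth correcting because baseline cytopenia is expressly allowed and small groups are shown side by side, but no decision rule depends on it.

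**What to change.** In SAP 7.2.1.2:
- Keep the current percentages and insert the word "denominator" in the sentence that defines them.
- For each test and direction, and for each threshold g (Grade 1 or more, 2 or more, 3 or more, and 4), add the number of subjects with worst post-baseline grade at or above g. Divide by subjects with a post-baseline value in the 30-day window whose baseline grade is below g or missing.
- Show Grade 3-to-4 worsening on its own line, over subjects at baseline Grade 3. In the invented example the two lines would read 5/33 for Grade 3 or more and 2/6 for Grade 3-to-4 worsening.

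Using thresholds gives each line one clear at-risk group and keeps a Grade 1-to-4 worsening visible in the lines for Grades 2 or more, 3 or more, and 4.

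In SAP 7.2.2, state the analysis set and window of the shift table. In SAP 7.7, replace the statement of no deviations and list any protocol laboratory table that will still not be produced, such as shifts by visit.

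The cost is a few sentences and one extra table or column, with a denominator that varies by test, direction and threshold. Baseline and worst grades are already derived for the planned tables, so no new data are needed. Some of the added percentages will be higher and some lower than those now planned, and the threshold lines will not sum across grades; a footnote should say so.

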#### **7.2.2. Shift in Relative to the Baseline**

Shift tables will be presented by showing change in severity grade from baseline to the worst grade postbaseline.

#### **7.3. Body Weight and Vital Signs**

A by-subject listing of body weight and vital signs will be provided by subject ID number and visit in chronological order. High or low values for vital signs will be flagged.

#### **7.4. Prior and Concomitant Medications**

Medications collected at screening and during the study will be coded using the current version of the World Health Organization (WHO) Drug dictionary.

##### **7.4.1. Prior Medications**

Prior medications are defined as any medications taken before a subject took the first study drug.

Prior medications will be summarized by Anatomical Therapeutic Chemical (ATC) drug class Level 2 and preferred name using the number and percentage of subjects for each treatment group and overall. A subject reporting the same medication more than once will be counted only once when calculating the number and percentage of subjects who received that medication. The summary will be ordered alphabetically by ATC medical class and then by preferred term in order of descending overall frequency within each ATC medical class. For drugs with the same frequency, sorting will be done alphabetically.

For the purposes of analysis, any medication with a start date prior to the first dosing date of study drug will be included in the prior medication summary regardless of when the stop date is. If a partial start date is entered the medication will be considered prior unless the month and year (if day is missing) or year (if day and month are missing) of the start date are after the first dosing date. Medications with a completely missing start date will be included in the prior medication summary, unless otherwise specified.

Summaries will be based on the Safety Analysis Set. No formal statistical testing is planned.

#### **7.4.2. Concomitant Medications**

Concomitant medications are defined as medications taken while a subject took study drug. Use of concomitant medications will be summarized by ATC drug class Level 2 and preferred name using the number and percentage of subjects for each treatment group. A subject reporting the same medication more than once will be counted only once when calculating the number and percentage of subjects who received that medication. The summary will be ordered alphabetically by ATC medical class and then by preferred term in descending overall frequency within each ATC medical class. For drugs with the same frequency, sorting will be done alphabetically.

For the purposes of analysis, any medications with a start date prior to or on the first dosing date of study drug and continued to be taken after the first dosing date, or started after the first dosing date but prior to or on the last dosing date of study drug will be considered concomitant medications. Medications started and stopped on the same day as the first dosing date or the last dosing date of study drug will also be considered concomitant. Medications with a stop date prior to the date of first dosing date of study drug or a start date after the last dosing date of study drug will be excluded from the concomitant medication summary. If a partial stop date is entered, any medication with the month and year (if day is missing) or year (if day and month are missing) prior to the date of first study drug administration will be excluded from the concomitant medication summary. If a partial start date is entered, any medication with the month and year (if day is missing) or year (if day and month are missing) after the study drug stop date will be excluded from the concomitant medication summary. Medications with completely missing start and stop dates will be included in the concomitant medication summary, unless otherwise specified. Summaries will be based on the Safety Analysis Set. No formal statistical testing is planned.

All concomitant medications (other than per-protocol study drugs) will be provided in a by-subject listing sorted by subject ID number and administration date in chronological order.

All prior and concomitant medications (other than per-protocol study drugs) will be provided in a by-subject listing sorted by subject ID number and administration date in chronological order.

#### **7.5. Electrocardiogram (ECG) Results**

Twelve (12)-lead ECGs reporting ventricular rate, PR, QRS, QT, and QTc intervals will be obtained at screening, safety monitoring visits and, if clinically indicated, during the course of the study.

ECG data including heart rate-corrected QT intervals (ie. corrected by Bazett's formula (QTcB) and Fridericia's formula (QTcF), will be presented in a by-subject listing sorted by subject ID number and exam date in chronological order. QTcB and QTcF will be derived as following formulas:

- Bazett formula:  $QTcB = QT / (RR)^{1/2}$
- Fridericia formula:  $QTcF = QT / (RR)^{1/3}$

where QT is measured in milliseconds, and  $RR = 60/\text{Heart Rate}$  (beats/min).

A by-subject listing of ECG results will be provided by subject ID number and visit in chronological order.

#### **7.6. Post Treatment Anti-Cancer Therapies**

All post treatment anti-cancer therapies (other than those allowed per-protocol) will be provided in a by-subject listing sorted by subject ID number and administration date in chronological order.

A summary of post treatment anti-cancer therapies will not be provided.

#### **7.7. Changes from Protocol-Specified Safety Analyses**

There are no deviations from the protocol-specified safety analyses.

## **8. PHARMACOKINETIC (PK) ANALYSES**

Plasma samples will be collected for concentrations of ENTO at protocol specified time points. Concentration of ENTO in plasma will be determined using a validated bioanalytical assay.

